5.4 Patient Consent

Patient / substitute decision maker (SDM) (for patients lacking decision-making capacity) consent must be obtained according to local institutional and/or University Human Experimentation Committee requirements prior to randomization into the ULTIMATE domain and start of the study intervention. It will be the responsibility of the local participating investigator to obtain the necessary institutional approval, and to indicate in writing to Ozmosis Research Inc. that such clearance has been obtained before the trial can commence at that centre. Sample English consent forms for the trial will be provided. A copy of the initial full board REB approval and approved consent forms must be sent to Ozmosis Research Inc. Consent process will be conducted as per Health Canada's notice "Management of Clinical Trials during the COVID-19 pandemic: Notice to clinical trial sponsors" updated May 6, 2021, FDA Guidance on Conduct of Clinical Trials of Medical Products during COVID-19 Public Health Emergency – Guidance for Industry, Investigators, and Institutional Review Boards March 2020 or REB recommendations.

Eligibility will be assessed by one of the site principal investigators or sub-investigators prior to entry into this domain. An explanation of the study and discussion of the expected side effects and full disclosure of the "informed consent" documents will then take place.

Each institution must have submitted all the necessary regulatory documentation to Ozmosis Research Inc. prior to randomizing consented and eligible patients via the REDCap database. General registration information can be found in the PRACTICAL Master Protocol.

6 STUDY PLAN

6.1 Study Schedule

Consenting eligible patients will be randomized to either the experimental group or the control group. Patients randomized to the experimental group will receive ultra-protective ventilation using ECMO. Patients requiring ventilation for longer periods may continue ventilation via ECMO or receive Conventional Lung-Protective Ventilation (LPV), as deemed necessary by the treating physician. Patients randomized to the control group will receive LPV. If the patient’s clinical status declines and meets the ECMO criteria for ventilation (as established by prior randomized clinical trials), they would be eligible to receive ECMO if their treating physician deems that appropriate. Please see sections 7.2 and 7.4 below.

Study procedures common to both groups will continue for the duration of the ICU stay up to day 30. We will collect daily data during mechanical ventilation until day 30. Thereafter, we will follow patients to the time of hospital discharge and record ICU/hospital survival. We will also assess health-related quality of life by telephone interview or via email 6 months after randomization.

6.2 Study Schema

Required Procedures	Pre-Ventilation (Baseline)	Daily*	Day 1	Day 3	Day 7	ICU Discharge	At 6 months post-randomization (Phone Visit)
Window	N/A	N/A	N/A	N/A	N/A	N/A	±14 days
Consent & Randomization ¹	X						
Demographics ²	X						
Medical History ³	X						
Vitals ⁴	X	X					
Hemodynamics ⁵	X	X					
Respiratory Data ⁶	X	X					
Hematology ⁷	X	X					
Biochemistry ⁸	X	X					

Arterial Blood Gases (ABG) ⁹	X	X					
Pregnancy Test (urine/serum)	X						
Optional: Blood Sample Collection ¹⁰	X			X	X	X	
For the Control Arm: Conventional Lung Protective Ventilation ¹¹ per section 7.2		X					
For the Experimental Arm: ECMO Intervention ¹² per section 7.1		X					
MV Readiness to Wean	X	X					
Spontaneous Breathing Trial ¹³		X					
Sweep Gas Off Trials (SGOTs) ¹⁴		X					
HrQOL, Modified Rankin Scale and Vital Status							X ¹⁵
Glasgow Coma Scale and Sofa Score	X	X					
Serious Adverse Events ¹⁶			X				
Concomitant Medications ¹⁷	X						

¹ Consent should be obtained prior to any study-specific baseline assessments and according to site institutional timelines. Randomization in the ULTIMATE domain will occur for consenting eligible patients once elastance has been estimated as high (≥ 2.5 cmH₂O/ml/kg PBW) per indicated eligibility criteria.

² Demographics include age, gender, height, and weight. Race and ethnicity will be reported only for patients who have consented to the collection of this data.

³ Hospital admission (date/time), ICU admission (date/time), APACHE IV, Charlson Comorbidity Index, COVID-19 infection status

⁴ Vitals include temperature, heart rate, respiratory rate, and blood pressure.

⁵ Hemodynamics include BP, PAPm, PCWP, SvO₂ and will reported in the database if collected.

⁶ Respiratory data include mode of ventilation, FiO₂, PEEP, PIP, RR, ventilation rate, tidal volume, plateau and driving pressure, oxygen saturation, and expiratory occlusion pressure (P_{occ}).

⁷ Hematology reporting on Hg, WBCs, and platelets. If not done daily per clinical standard-of-care procedures, sites are not required to have these tests done exclusively for research purposes, and this will not be considered a protocol deviation.

⁸ Biochemistry will include reporting the following values: INR, PTT, activated clotting time, Fibrinogen, Antithrombin III, D-Dimers, plasma-free hemoglobin, sodium, glucose, creatinine, albumin, bilirubin, potassium, bicarbonate, creatinine kinase,

troponin, phosphate, total calcium. If not done daily per clinical standard-of-care procedures, sites are not required to have these tests done exclusively for research purposes, and this will not be considered a protocol deviation.

⁹ ABG testing will include the following parameters: pH, PaCO₂, HCO₃, base excess, SaO₂, lactate, hemoglobin.

¹⁰ Blood sample collection is optional and will proceed only if patient or their SDM signs the optional consent form.

¹¹ Patient will be on mechanical ventilation, regardless of randomization, and will be assessed daily for readiness to wean.

¹² ECMO will be administered once patient has stabilized on initial MV settings and will be maintained for at least 48 hours. If patient is unsuccessful on Sweep Gas Off Trials (SGOTs) post 48 hours, then ECMO will continue until no longer needed and per the discretion of the treating physician.

¹³ Spontaneous breathing trials (SBTs) will be conducted only when patient is deemed ready for weaning from MV and per standard of care and/or institutional guidelines.

¹⁴ Patients who have received ≥ 48 hours of ECMO therapy will be assessed daily for ECMO discontinuation with SGOTs. This assessment will be considered successful if patients tolerate SGOTs for ≥ 12 hrs with no significant hypoxemia, respiratory acidosis, or work of breathing.

¹⁵ HrQOL questionnaires (ADL and EQ-5D-5L) as well as the Modified Rankin Scale (MRS) will be administered via phone or e-mail at 6 months. Vital status (patient dead or alive) will also be reported at this timepoint.

¹⁶ SAEs will be reported at the start of randomization and for a period of up to 30 days, or while in ICU, whichever is shorter.

¹⁷ Concomitant medications listed in section 6 will only be captured, if taken.

*Daily data common to both groups will be collected for the duration of intervention administration and ICU stay and up to day 30.

6.3 Optional Correlative Sample Collection

Blood sample collection for the assessment of biomarkers and other future research studies will occur at the time points indicated within the Study Schema. It is not mandatory for all sites to participate in the collection of correlative samples and each sites' willingness and ability to participate will be discussed individually. In participating sites, patients will be provided with an informed consent form to review and indicate their willingness to participate in this optional sample collection.

Further details are available in the MOP.

7 CONCOMITANT MEDICATION/ PROCEDURES

The administration of the following concomitant medications will be collected for study purposes from time of consent to time of ICU discharge or for 30 days, whichever is shorter.

- Neuromuscular blocking agents (e.g., rocuronium, cisatracurium)
- Sedatives (e.g., propofol, fentanyl, midazolam)
- Corticosteroids (e.g., methylprednisolone, prednisone, dexamethasone)
- Inotropes (e.g., dobutamine, milrinone)
- Vasopressors (e.g., norepinephrine, vasopressin, epinephrine)
- Diuretics (e.g., furosemide, metolazone)

Additionally, the following procedures are to be documented:

- Prone positioning
- Renal replacement therapy

8 TRIAL INTERVENTIONS

Our goal is to study ultra-protective ventilation (i.e., low driving pressure, tidal volume, and respiratory rate) facilitated by ECMO devices compared to Conventional Lung Protective Ventilation.

8.1 Experimental Group: Ultra-protective Ventilation using ECMO devices

Patients randomized to the experimental group will receive VV-ECMO with cannula(e) configuration at the discretion of the treating centre. We will employ an explicit protocol outlined below that draws heavily on our previous ECMO protocols,[14, 19] and on expert consensus.[15]

8.1.1 Stabilization and ECMO Initiation

If not already done, patients will be deeply sedated to a Sedation Assessment Scale (SAS) = 1 and then be paralyzed with a neuromuscular blocking agent (NMBA). Baseline usual care standard ventilation will then be set as follows:

- Mode: Volume Assist-Control
- FiO₂ 1.0;
- PEEP 10-15 cm H₂O or higher as needed to maintain SpO₂>92%;
- V_T = 6 ml/kg PBW and adjusted to maintain P_{PLAT} ≤ 30 cm H₂O
- Inspiratory to expiratory (I:E) ratio 1:1 to 1:3, avoiding auto-PEEP
- Respiratory rate set to match previous minute ventilation to maximum of 35 bpm and targeting a pH above 7.15

These initial adjustments may occur over a period of a few minutes to a couple of hours, depending upon the baseline V_T and the ability of the patient to tolerate sudden changes. In keeping with routine clinical practices, an arterial blood gas should be drawn within 1 hour of transitioning onto the study protocol to assess both oxygenation and ventilation.

As soon as the patient is stable on these standard settings, the clinical team will measure the patient's respiratory elastance using the following equation:

$$Elastance = \frac{Driving\ Pressure}{\frac{Tidal\ Volume}{PBW}} = \frac{P_{plat} - PEEP\ total}{\frac{VT}{PBW}}$$

If the patient's static driving pressure is 15 cmH₂O or lower, then re-assess patient within a 12-hour timeline for ECMO initiation whilst keeping the patient deeply sedated and paralyzed. If patient's static ΔP is 16 cmH₂O or higher, then proceed with cannulation and connection to the VV-ECMO circuit using sterile technique and monitoring according to usual practice (e.g. ultrasound-guided puncture, radiography, trans-esophageal echocardiography (TEE), or

fluoroscopic cannula positioning). We recommend use of the study-supplied dual-lumen bicaval Crescent cannula connected to the Nautilus oxygenator, but the clinical team may choose any VV-ECMO configuration that facilitates 3-5 L/min blood flow.

VV-ECMO will then be initiated with pump speed set to deliver blood flow of 3-5 L/min and sweep gas flow of 1 L/min of 100% oxygen.

The mechanical ventilator will then be adjusted as follows:

- Mode: Pressure Control
- FiO₂ 0.5
- Set Driving Pressure to 10
- PEEP 10-15 cm H₂O
- Inspiratory time 0.7-1 second
- Respiratory rate 10

As per usual care, an arterial blood gas will be drawn after 15-30 minutes, and sweep gas flow will be adjusted to target a PaCO₂ of 40-60 mmHg; if the baseline PaCO₂ is above 60 we will target lowering it slowly by no more than 10-20 per 12 hours.[19] We will maintain a FdO₂ of 1.0 on the circuit and adjust blood flow rates to maintain SpO₂ 92-97%.

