5.1 Patient population

This domain will enrol patients in the following platform defined state;

- Intubated patients, not on extracorporeal life support (ECLS), with high normalized respiratory system elastance (≥ 2.5 cm H₂O/(ml/kg predicted body weight)).

Patients must meet both the PRACTICAL platform eligibility criteria (section 3.2) and the domain-specific ULTIMATE eligibility criteria (section 3.3) prior to randomization. Any questions about eligibility criteria must be addressed prior to patient randomization.

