5.3.2 Exclusion Criteria

1. Patients over 65 years of age.
2. Currently receiving any form of ECMO (ex. venovenous, venoarterial, or hybrid configuration).
3. $\Delta P_{L-dyn} \leq 20$ or Static $\Delta P \leq 15$ cmH₂O while receiving V_T 6mL/kg (i.e. normalized elastance < 2.5 cmH₂O/mL/kg).
4. Chronic hypercapnic respiratory failure defined as $\text{PaCO}_2 > 60$ mmHg in the outpatient setting.
5. Home mechanical ventilation (non-invasive ventilation or via tracheotomy), not CPAP.
6. Actual body weight exceeding 1kg per centimeter of height.
7. More than 48 hours have passed since meeting inclusion criteria.
8. Severe hypoxemia with $\text{PaO}_2/\text{FiO}_2 < 80$ mmHg for > 6 hours at time of screening.
9. Severe hypercapnic respiratory failure with $\text{pH} < 7.15$ and $\text{PaCO}_2 > 60$ mmHg for > 6 hours at time of screening.
10. Expected mechanical ventilation duration < 48 hours at time of screening.
11. Confirmed diffuse alveolar hemorrhage from vasculitis.
12. Contraindications to limited anticoagulation (ex. active GI bleeding, bleeding diathesis).
13. Pregnancy—due to unknown effects of PaCO_2 changes on placental blood flow.
14. Respiratory failure known or suspected to be caused by COVID-19.

Eligible non-randomized patients will be identified and reasons for non-enrolment classified as:

1. Lack of consent from patient or substitute decision maker (specifying reason);
2. Refusal from attending physician (specifying reason);
3. Enrolment in a confounding RCT;
4. Research coordinator or device not available.

To better characterize the generalisability of our randomized population, baseline, demographic, and outcome data will be recorded on all eligible non-randomized patients.

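### The ECMO start rule in section 8.1.1 cannot be met at PEEP 15 or above, does not match the entry criteria, and patients who never start ECMO are not counted

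*Protocol*

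**What the plan says.** **Entry.** Section 5.1 takes patients "with high normalized respiratory system elastance", defined as 2.5 cmH₂O/(mL/kg) or more, and footnote 1 of the schema in section 6.2 uses the same cut-off for randomisation. Exclusion 3 in section 5.3.2 removes patients with a static driving pressure of 15 or less at a tidal volume of 6 mL/kg (or a dynamic transpulmonary value of 20 or less) and explains this as "normalized elastance < 2.5".

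**After allocation, experimental group only.** Section 8.1.1 sets ventilation on FiO₂ 1.0 with "PEEP 10-15 cm H₂O or higher as needed to maintain SpO₂>92"% and "V_T = 6 ml/kg PBW and adjusted to maintain P_{PLAT} ≤ 30 cm H₂O". The team then calculates elastance, with driving pressure defined as plateau pressure minus total PEEP. The decision itself rests on unadjusted driving pressure. For a low reading the text is "static driving pressure is 15 cmH₂O or lower, then re-assess patient within a 12-hour timeline for ECMO initiation", with deep sedation and paralysis continued. For a high reading it is "If patient's static ΔP is 16 cmH₂O or higher, then proceed with cannulation".

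**Elsewhere.** Sections 6.1 and 8.1 say that the experimental group will receive ECMO and do not mention this condition. Section 8.4 lists experimental patients who stop ECMO too early as deviating crossovers. Section 10.7 defines experimental deviations by tidal volume above 8 mL/kg, plateau pressure above 30 or dynamic transpulmonary driving pressure above 23. Section 10.13 sets the success criteria: more than 80% of patients adherent, and fewer than 10% crossing over when the protocol does not allow it.

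**The concern.** The quantity that triggers ECMO is limited by the settings under which it is measured. Lowering tidal volume to respect the plateau limit lowers driving pressure but leaves elastance unchanged. A patient can therefore qualify for the trial on elastance and miss the start rule because the team followed the ventilation instructions. The entry threshold and the start threshold also differ when both are read at 6 mL/kg.

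This pilot exists to show that the assigned strategy can be delivered. If some experimental patients wait for ECMO or never receive it, separation between the arms shrinks under the intention-to-treat analysis. Section 3.2 attributes the neutral result of an earlier low-flow CO₂ removal trial to too little separation. Under section 4.2 the pilot patients may also roll into the definitive trial. The feasibility measures would not show the problem, because no section says how to count a patient who never starts.

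**Working it through.** **Inputs.** Plateau limit 30, PEEP 10–15 or higher, tidal volume (VT) 6 mL/kg adjusted to the plateau limit, start at 16 or more, re-assess at 15 or less (all section 8.1.1); elastance cut-off 2.5 (sections 5.1 and 6.2); driving-pressure cut-off 15 at 6 mL/kg (section 5.3.2); 72 patients (section 10.1) allocated 1:1 (section 10.15).

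**1. The protocol's own equivalence.** Elastance = driving pressure ÷ (VT per kg) = 15/6 = 2.50. The figure is reproduced. However, 15 or less corresponds to 2.50 or less, not to below 2.5, so a patient at exactly 2.5 is included by sections 5.1 and 6.2 and excluded by the pressure limit in section 5.3.2.

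**2. Highest possible driving pressure = 30 − PEEP.**

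| PEEP | Maximum driving pressure | Can 16 be reached? |
|---|---|---|
| 10 | 20 | yes |
| 12 | 18 | yes |
| 13 | 17 | yes |
| 14 | 16 | only at plateau exactly 30 |
| 15 | 15 | no |
| 16 | 14 | no |
| 18 | 12 | no |
| 20 | 10 | no |

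Any intrinsic PEEP lowers these maxima, because total PEEP is subtracted. A patient with driving pressure above 15 at 6 mL/kg and PEEP of 15 or more has a plateau above 30, so VT must be reduced and driving pressure falls to 15 or below.

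**3. Worked patients.** VT = the smaller of 6 and (30 − PEEP)/elastance; driving pressure = elastance × VT.

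| Elastance | PEEP | Plateau at 6 mL/kg | VT after adjustment | Driving pressure | Result |
|---|---|---|---|---|---|
| 3.0 | 12 | 30 | 6.00 | 18 | start |
| 3.0 | 14 | 32 | 5.33 | 16 | start |
| 3.0 | 15 | 33 | 5.00 | 15 | re-assess |
| 4.0 | 14 | 38 | 4.00 | 16 | start |
| 4.0 | 15 | 39 | 3.75 | 15 | re-assess |

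**4. Entry against start at 6 mL/kg.** The start rule needs elastance of at least 16/6 = 2.67. A patient with elastance 2.6 has driving pressure 2.6 × 6 = 15.6. That patient is eligible, yet even at PEEP 10 (plateau 25.6, well under the limit) the reading is above 15 and below 16, which neither branch covers. The gap runs from 2.50, or just above it, to just under 2.67.

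**5. What the feasibility counts would show.** The patient held at elastance 3.0 and PEEP 15 has VT 5 and plateau 30, so breaches neither the VT nor the plateau limit in section 10.7. Under section 8.4 that patient has not stopped ECMO, because it was never started. One patient is 1/36 = 2.8% of the experimental arm (72/2 = 36). If the 10% limit is taken over all 72, it allows 7 crossovers (7/72 = 9.7%) and not 8 (8/72 = 11.1%). Eight never-started patients would be 8/36 = 22% of the arm. They would breach the limit if counted, but the current definitions do not clearly count any of them. This is an illustration, not a forecast.

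**The case against.** **PEEP of 15 is the edge of the range.** Higher PEEP is used only as oxygenation requires, on FiO₂ 1.0, and patients with prolonged PaO₂/FiO₂ below 80 are excluded. The elastance 3.0 patient meets the rule at PEEP 12 to 14. This stands: the documents give no reason to think that PEEP of 15 or more will be common, and the number affected is unknown. But 15 lies inside the stated range and the text expressly permits more.

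**The text says re-assess.** A reader might infer that these patients are barred from ECMO. The protocol does not say so: they are delayed, and PEEP may be lower at the next measurement. What remains is that an unchanged state gives the same result and no outcome is then stated.

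**The stiffest lungs.** A reader might infer that the stiffest lungs lose out most. The arithmetic does not support this. At PEEP 15 or above every elastance is affected alike. At PEEP 14 or below the stiffest lungs can reach 16, and those just above the entry threshold cannot.

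**A check in one arm is not a fault in itself.** An ECMO start check can exist only where ECMO is assigned, and re-measuring under paralysis is an intelligible choice. It does not follow that the measurement must be completed before randomisation in both arms; that is a debatable design and clinical decision. Nor are patients lost from analysis, since section 10.12 already keeps all randomised patients under intention to treat.

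**Whole-number readings.** If pressures are recorded in whole cmH₂O at exactly 6 mL/kg, above 15 means 16 or more, and the gap in step 4 closes except at exactly 15. The protocol does not state this precision, and elastance is not confined to such steps. The PEEP conflict is unaffected.

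**Conclusion.** The point holds as an internal contradiction. Under the stabilisation settings of section 8.1.1, the ECMO start rule cannot be satisfied at PEEP 15 or above, and at 6 mL/kg it asks for an elastance of 2.67 where entry asks for 2.5. The first result is exact and assumes only that the plateau limit is respected when the reading is taken. The second assumes unchanged mechanics between entry and that reading, and pressures not restricted to whole numbers.

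The consequence is delayed or undelivered ECMO in an unknown number of experimental patients, with diluted separation under intention to treat. Because sections 8.4, 10.7 and 10.13 do not classify a patient who never starts, the adherence and crossover criteria could be declared met regardless. The documents do not support a claim of exclusion from ECMO, of selective loss of the stiffest lungs, or of bias from removing patients from the analysis.

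**What to change.** 1. Reconcile sections 5.1, 5.3.2 (exclusion 3), 6.2 (footnote 1) and 8.1.1 so that entry and ECMO start use a consistent quantity, cut-off and set of measurement conditions, compatible with the plateau and PEEP settings. This includes the treatment of exactly 2.5 and of readings between 15 and 16. Which quantity and threshold to use is the sponsor's clinical choice.
2. State in section 8.1.1 what follows when the re-assessment again falls below the start threshold.
3. In sections 8.4 and 10.13, classify experimental patients who never start ECMO, say whether they count towards the 10% crossover limit and the adherence outcome, and report their number and reasons.

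The cost is amendment wording plus alignment of the eligibility and crossover forms. No extra patients are needed, and the analysis population does not change.

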8.1.2 Maintenance and Weaning of Ultra-Protective Ventilation

Deep sedation, paralysis, and these low-intensity mechanical ventilation settings will be maintained for at least 48 hours after ECMO initiation. The clinical team will make adjustments to the VV-ECMO settings to maintain the same PaCO₂, pH and PaO₂ and SpO₂ targets as above. These adjustments to VV-ECMO sweep gas or blood flow will be dictated by ABG results drawn as clinically indicated.

On study day 3, patients will then enter the maintenance and weaning phase – neuromuscular blockade will be discontinued, and lighter sedation levels (SAS 2-3) will be targeted unless otherwise decided by the attending physician.

During the first 7 days after randomization and once neuromuscular blockade is stopped and patients are making spontaneous breathing efforts, we will use sweep gas flow (primary) and sedation (secondary) to modulate spontaneous efforts to maintain low intensity ventilation, targeting the estimated dynamic trans-pulmonary driving pressure (ΔP_{L-dyn}) and tidal volume.

Clinicians will measure patient respiratory effort by calculating ΔP_{occ} (which is always zero or negative):[26]

- Perform expiratory hold and record trough pressure with next effort (record as = PEEP if no efforts made)
- Calculate $\Delta P_{occ} = \text{trough pressure} - \text{PEEP}$
- Calculate $\Delta P_{L-dyn} = (\text{Peak airway pressure} - \text{PEEP}) - 0.67 \times \Delta P_{occ}$

To maintain $\Delta P_{L-dyn} \leq 23$ cm H₂O while maintaining a V_T of 8 ml/kg PBW or lower, the treating team will adjust in the following order: a) the mechanical ventilator, b) the sweep gas flow, and c) sedation levels. After day 7 driving pressure and V_T targets, as well as sweep gas settings will be determined by the attending physician.

We will wean ECMO prior to liberating from mechanical ventilation and provide explicit protocols for weaning ECMO (See Manual of Procedures). Briefly, patients will be assessed daily for ability to discontinue ECMO – all patients who are not paralyzed and are breathing spontaneously on sweep gas flow of 4 L/min or less, and who are receiving an FiO₂ of ≤ 0.6 on the mechanical ventilator with a PaO₂/FiO₂ > 150 will undergo a trial of sweep gas off on ECMO. ECMO will be discontinued if patients tolerate sweep gas off for at least 12 hours (i.e., no significant hypoxemia, respiratory acidosis, or work of breathing).

Anticoagulation with intravenous heparin infusion during VV-ECMO will be recommended at a level to target aPTT 1.5-2 times normal but will be ultimately managed at the discretion of the attending physician. After 14 days, all study-mandated procedures related to ECMO will cease and ongoing management will be determined by the attending physician.

